### **5.3.5.9 Lack of Efficacy or Worsening of Cancer**

Events that are clearly consistent with the expected pattern of progression of the underlying disease should not be recorded as adverse events. These data will be captured as efficacy assessment data only. In most cases, the expected pattern of progression will be based on RECIST v1.1 or PCWG3 criteria. In rare cases, the determination of clinical progression will be based on symptomatic deterioration. However, every effort should be made to document progression through use of objective criteria. If there is any uncertainty as to whether an event is due to disease progression, it should be reported as an adverse event.

### **5.3.5.10 Hospitalization or Prolonged Hospitalization**

Any adverse event that results in hospitalization (i.e., inpatient admission to a hospital) or prolonged hospitalization should be documented and reported as a serious adverse event (per the definition of serious adverse event in Section 5.2.2), except as outlined below.

An event that leads to hospitalization under the following circumstances should not be reported as an adverse event or a serious adverse event:

- Hospitalization for respite care
- Planned hospitalization required by the protocol (e.g., for study drug administration)
- Hospitalization for a preexisting condition, provided that all of the following criteria are met:
  - The hospitalization was planned prior to the study or was scheduled during the study when elective surgery became necessary because of the expected normal progression of the disease
  - The patient has not experienced an adverse event
- Hospitalization due solely to progression of the underlying cancer

An event that leads to hospitalization under the following circumstances is not considered to be a serious adverse event, but should be reported as an adverse event instead:

- Hospitalization that was necessary because of patient requirement for outpatient care outside of normal outpatient clinic operating hours

#### **5.4 IMMEDIATE REPORTING REQUIREMENTS FROM INVESTIGATOR TO SPONSOR**

Certain events require immediate reporting to allow the Sponsor to take appropriate measures to address potential new risks in a clinical trial. The investigator must report such events to the Sponsor immediately; under no circumstances should reporting take place more than 24 hours after the investigator learns of the event. The following is a list of events that the investigator must report to the Sponsor within 24 hours after learning of the event, regardless of relationship to study drug:

- Serious adverse events (defined in Section 5.2.2; see Section 5.4.2 for details on reporting requirements)
- Adverse events of special interest (defined in Section 5.2.3; see Section 5.4.2 for details on reporting requirements)
- Pregnancies (see Section 5.4.3 for details on reporting requirements)
- Overdoses, medication errors, drug abuse, or drug misuse (see Section 5.4.4 for details on reporting requirements)

The investigator must report new significant follow-up information for these events to the Sponsor immediately (i.e., no more than 24 hours after becoming aware of the information). New significant information includes the following:

- New signs or symptoms or a change in the diagnosis
- Significant new diagnostic test results
- Change in causality based on new information
- Change in the event's outcome, including recovery
- Additional narrative information on the clinical course of the event

Investigators must also comply with local requirements for reporting serious adverse events to the local health authority and IRB/EC.

## **5.4.2 Reporting Requirements for Serious Adverse Events and Adverse Events of Special Interest**

### **5.4.2.1 Events that Occur prior to Study Drug Initiation**

After informed consent has been obtained but prior to initiation of study drug, only serious adverse events caused by a protocol-mandated intervention should be reported. The paper Clinical Trial Serious Adverse Event/Adverse Event of Special Interest Reporting Form provided to investigators should be completed and submitted to the Sponsor or its designee immediately (i.e., no more than 24 hours after learning of the event), either by faxing or by scanning and emailing the form using the fax number or email address provided to investigators.

### **5.4.2.2 Events that Occur after Study Drug Initiation**

After initiation of study drug, serious adverse events and adverse events of special interest will be reported until 28 days after the final dose of study drug. Investigators should record all case details that can be gathered immediately (i.e., within 24 hours after learning of the event) on the Adverse Event eCRF and submit the report via the electronic data capture (EDC) system. A report will be generated and sent to Roche Safety Risk Management by the EDC system.

In the event that the EDC system is unavailable, the paper Clinical Trial Serious Adverse Event/Adverse Event of Special Interest Reporting Form provided to investigators should be completed and submitted to the Sponsor or its designee immediately (i.e., no more than 24 hours after learning of the event), either by faxing or by scanning and emailing the form using the fax number or email address provided to investigators. Once the EDC system is available, all information will need to be entered and submitted via the EDC system.

Instructions for reporting serious adverse events that occur > 28 days after the final dose of study treatment are provided in Section 5.6.

### **5.4.3 Reporting Requirements for Pregnancies**

#### **5.4.3.1 Pregnancies in Female Patients**

Female patients of childbearing potential will be instructed to immediately inform the investigator if they become pregnant during the study or within 28 days after the final dose of ipatasertib or within 6 months after the last dose of rucaparib. A paper Clinical Trial Pregnancy Reporting Form should be completed and submitted to the Sponsor or its designee immediately (i.e., no more than 24 hours after learning of the pregnancy), either by faxing or by scanning and emailing the form using the fax number or email address provided to investigators. Pregnancy should not be recorded on the Adverse Event eCRF. The investigator should discontinue study drug and counsel the patient, discussing the risks of the pregnancy and the possible effects on the fetus. Monitoring of the patient should continue until conclusion of the pregnancy. Any serious adverse events associated with the pregnancy (e.g., an event in the fetus, an event in the mother during or after the pregnancy, or a congenital anomaly/birth defect in the child) should be reported on the Adverse Event eCRF. In addition, the investigator will submit a Clinical Trial Pregnancy Reporting Form when updated information on the course and outcome of the pregnancy becomes available.

#### **5.4.3.2 Pregnancies in Female Partners of Male Patients**

Male patients will be instructed through the Informed Consent Form to immediately inform the investigator if their partner becomes pregnant during the study or within 28 days after the final dose of ipatasertib or within 6 months after the last dose of rucaparib. A paper Clinical Trial Pregnancy Reporting Form should be completed and submitted to the Sponsor or its designee immediately (i.e., no more than 24 hours after learning of the pregnancy), either by faxing or by scanning and emailing the form using the fax number or email address provided to investigators. Attempts should be made to collect and report details of the course and outcome of any pregnancy in the partner of a male patient exposed to study drug. When permitted by the site, the pregnant partner would need to sign an Authorization for Use and Disclosure of Pregnancy Health Information to allow for follow-up on her pregnancy. If the authorization has been signed, the investigator should submit a Clinical Trial Pregnancy Reporting Form when updated information on the course and outcome of the pregnancy becomes available. An investigator who is contacted by the male patient or his pregnant partner may provide information on the risks of the pregnancy and the possible effects on the fetus, to support an informed decision in cooperation with the treating physician and/or obstetrician.

#### **5.4.3.3 Abortions**

*A spontaneous* abortion should be classified as a serious adverse event (as the Sponsor considers abortions to be medically significant), recorded on the Adverse Event eCRF,

and reported to the Sponsor immediately (i.e., no more than 24 hours after learning of the event; see Section 5.4.2).

*If a therapeutic or elective abortion was performed because of an underlying maternal or embryofetal toxicity, the toxicity should be classified as a serious adverse event, recorded on the Adverse Event eCRF, and reported to the Sponsor immediately (i.e., no more than 24 hours after learning of the event; see Section 5.4.2). A therapeutic or elective abortion performed for reasons other than an underlying maternal or embryofetal toxicity is not considered an adverse event.*

*All abortions should be reported as pregnancy outcomes on the paper Clinical Trial Pregnancy Reporting Form.*

#### **5.4.3.4 Congenital Anomalies/Birth Defects**

Any congenital anomaly/birth defect in a child born to a female patient exposed to study drug or the female partner of a male patient exposed to study drug should be classified as a serious adverse event, recorded on the Adverse Event eCRF, and reported to the Sponsor immediately (i.e., no more than 24 hours after learning of the event; see Section 5.4.2).

#### **5.4.4 Reporting Requirements for Cases of Overdose, Medication Error, Drug Abuse, or Drug Misuse**

Overdose (accidental or intentional), medication error, drug abuse, and drug misuse (hereafter collectively referred to as "special situations"), are defined as follows:

- Accidental overdose: accidental administration of a drug in a quantity that is higher than the assigned dose
- Intentional overdose: intentional administration of a drug in a quantity that is higher than the assigned dose
- Medication error: accidental deviation in the administration of a drug
  - In some cases, a medication error may be intercepted prior to administration of the drug.
- Drug abuse: intentional excessive use of a drug that may lead to addiction or dependence, physical harm, and/or psychological harm
- Drug misuse: intentional deviation in the administration of a drug that does not qualify as drug abuse

In cases where drug is to be self-administered by the patient, drug misuse could involve the drug being administered to someone other than the patient.

Special situations are not in themselves adverse events, but may result in adverse events. Each adverse event associated with a special situation should be recorded separately on the Adverse Event eCRF. If the associated adverse event fulfills seriousness criteria, the event should be reported to the Sponsor immediately (i.e., no more than 24 hours after learning of the event; see Section 5.4.2). For

ipatasertib, adverse events associated with special situations should be recorded as described below for each situation:

- Accidental overdose: Enter the adverse event term. Check the "Accidental overdose" and "Medication error" boxes.
- Intentional overdose: Enter the adverse event term. Check the "Intentional overdose" box. If drug abuse is suspected, check the "Drug abuse" box. If drug abuse is not suspected, check the "Drug misuse" box.
- Medication error that does not qualify as an overdose: Enter the adverse event term. Check the "Medication error" box.
- Medication error that qualifies as an overdose: Enter the adverse event term. Check the "Accidental overdose" and "Medication error" boxes.
- Drug abuse that does not qualify as an overdose: Enter the adverse event term. Check the "Drug abuse" box.
- Drug abuse that qualifies as an overdose: Enter the adverse event term. Check the "Intentional overdose" and "Drug abuse" boxes.
- Drug misuse that does not qualify as an overdose: Enter the adverse event term. Check the "Drug misuse" box.
- Drug misuse that qualifies as an overdose: Enter the adverse event term. Check the "Intentional overdose" and "Drug misuse" boxes.

In addition, all special situations associated with ipatasertib, regardless of whether they result in an adverse event, should be recorded on the Adverse Event eCRF and reported to the Sponsor immediately (i.e., no more than 24 hours after learning of the event).

Special situations should be recorded as described below:

- Accidental overdose: Enter the drug name and "accidental overdose" as the event term. Check the "Accidental overdose" and "Medication error" boxes.
- Intentional overdose: Enter the drug name and "intentional overdose" as the event term. Check the "Intentional overdose" box. If drug abuse is suspected, check the "Drug abuse" box. If drug abuse is not suspected, check the "Drug misuse" box.
- Medication error that does not qualify as an overdose: Enter the name of the drug administered and a description of the error (e.g., wrong dose administered, wrong dosing schedule, incorrect route of administration, wrong drug, expired drug administered) as the event term. Check the "Medication error" box.
- Medication error that qualifies as an overdose: Enter the drug name and "accidental overdose" as the event term. Check the "Accidental overdose" and "Medication error" boxes. Enter a description of the error in the additional case details.
- Intercepted medication error: Enter the drug name and "intercepted medication error" as the event term. Check the "Medication error" box. Enter a description of the error in the additional case details.
- Drug abuse that does not qualify as an overdose: Enter the drug name and "drug abuse" as the event term. Check the "Drug abuse" box.

- Drug abuse that qualifies as an overdose: Enter the drug name and "intentional overdose" as the event term. Check the "Intentional overdose" and "Drug abuse" boxes.
- Drug misuse that does not qualify as an overdose: Enter the drug name and "drug misuse" as the event term. Check the "Drug misuse" box.
- Drug misuse that qualifies as an overdose: Enter the drug name and "intentional overdose" as the event term. Check the "Intentional overdose" and "Drug misuse" boxes.
- Drug administered to someone other than the patient: Enter the drug name and "patient supplied drug to third party" as the event term. Check the "Drug misuse" box.

As an example, an accidental overdose that resulted in a headache would require the completion of two Adverse Event eCRF pages, one to report the accidental overdose and one to report the headache. The "Accidental overdose" and "Medication error" boxes would need to be checked on both eCRF pages.

## **5.5 FOLLOW-UP OF PATIENTS AFTER ADVERSE EVENTS**

### **5.5.1 Investigator Follow-Up**

The investigator should follow each adverse event until the event has resolved to baseline grade or better, the event is assessed as stable by the investigator, the patient is lost to follow-up, or the patient withdraws consent. Every effort should be made to follow all serious adverse events considered to be related to study drug or trial-related procedures until a final outcome can be reported.

During the study period, resolution of adverse events (with dates) should be documented on the Adverse Event eCRF and in the patient's medical record to facilitate source data verification.

All pregnancies reported during the study should be followed until pregnancy outcome.

### **5.5.2 Sponsor Follow-Up**

For serious adverse events, adverse events of special interest, and pregnancies, the Sponsor or a designee may follow up by telephone, fax, email, and/or a monitoring visit to obtain additional case details and outcome information (e.g., from hospital discharge summaries, consultant reports, autopsy reports) in order to perform an independent medical assessment of the reported case.

## **5.6 ADVERSE EVENTS THAT OCCUR AFTER THE ADVERSE EVENT REPORTING PERIOD**

After the end of the adverse event reporting period (defined as 28 days after the final dose of study drug), all deaths, regardless of cause, should be reported through use of the Long-Term Survival Follow-Up eCRF.

In addition, if the investigator becomes aware of a serious adverse event that is believed to be related to prior exposure to study drug, the event should be reported through use of the Adverse Event eCRF. However, if the EDC system is not available, the investigator should report these events directly to the Sponsor or its designee, either by faxing or by scanning and emailing the paper Clinical Trial Serious Adverse Event/Adverse Event of Special Interest Reporting Form using the fax number or email address provided to investigators.

## **5.7 EXPEDITED REPORTING TO HEALTH AUTHORITIES, INVESTIGATORS, INSTITUTIONAL REVIEW BOARDS, AND ETHICS COMMITTEES**

The Sponsor will promptly evaluate all serious adverse events and adverse events of special interest against cumulative product experience to identify and expeditiously communicate possible new safety findings to investigators, IRBs, ECs, and applicable health authorities based on applicable legislation.

To determine reporting requirements for single adverse event cases, the Sponsor will assess the expectedness of these events using the following reference documents:

- Ipatasertib Investigator's Brochure
- Rucaparib Investigator's Brochure

The Sponsor will compare the severity of each event and the cumulative event frequency reported for the study with the severity and frequency reported in the applicable reference document.

Reporting requirements will also be based on the investigator's assessment of causality and seriousness, with allowance for upgrading by the Sponsor as needed.

## **6. STATISTICAL CONSIDERATIONS AND ANALYSIS PLAN**

The primary analysis will be based on patients data collected through study discontinuation or at the end of study. All analyses will be conducted using the safety-evaluable population, defined as all patients who receive any amount of study treatment.

No formal hypothesis testing is planned. The safety, tolerability, clinical activity, and pharmacokinetics of ipatasertib, and its metabolite G-037720, with rucaparib will be described and summarized.

Data will be described and summarized as warranted by sample size. That is, listings may be used in lieu of tables in the event of small sample size.

Descriptive statistics will be used to summarize the safety and clinical activity of treatment regimens. Continuous variables will be summarized using means, standard

deviation, median, and range; categorical variables will be summarized using count and percentage.

## 6.1 DETERMINATION OF SAMPLE SIZE

There is no formal hypothesis testing planned. The determination of sample size for each part is described below.

For Part 1 (Dose-Escalation Phase), approximately 24 patients are planned to be enrolled based on the dose-escalation rules.

For Part 2 (Dose-Expansion Phase), approximately 30 patients with advanced prostate cancer who have had at least one line of prior therapy with second-generation AR-receptor targeted agents (e.g., abiraterone, enzalutamide, apalutamide) are planned to be enrolled. No formal statistical hypothesis testing is planned. Instead, the analysis here is for hypothesis generation, and the emphasis is on estimations. To evaluate the primary endpoint of PSA response rate, the analyses will be based on patients enrolled in Part 2. [Table 16](#) shows estimated PSA response rate and its 95% CI based on the Clopper-Pearson method given various observed numbers of responders among the 30 patients. Thirty patients provide reasonably reliable estimates for hypothesis generation.

**Table 16 Estimated PSA Response Rate and Its 95% CI for 30 Patients**

Number of Responders	Response Rate (%)	95% CI (%)
6	20	7.71, 38.57
9	30	14.73, 49.40
12	40	22.66, 59.40
15	50	31.30, 68.70
18	60	40.60, 70.34
21	70	50.60, 85.27
24	80	61.43, 92.29

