#### **6.4.1 Primary Efficacy Endpoint for Patients with Prostate Cancer**

For patients with prostate cancer, PSA response rate is defined as the proportion of patients achieving a PSA decline  $\geq 50\%$  from baseline. Patients without a post-baseline PSA assessment will be considered non-responders. The PSA response rate will be calculated, and the 95% CI will be estimated using the Clopper-Pearson method.

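### Table 16 prints the upper 95% limit for 18 of 30 responders as 70.34%; the Clopper-Pearson value is 77.34%, so that row understates the interval width by 7 points

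*Combined protocol and SAP*

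**What the plan says.** Section 6.1 plans to enrol in Part 2 "approximately 30 patients with advanced prostate cancer who have had at least one line of prior therapy" with a second-generation androgen-receptor agent. On the basis for that number it says: "No formal statistical hypothesis testing is planned. Instead, the analysis here is for hypothesis generation, and the emphasis is on estimations". It then points to Table 16, which "shows estimated PSA response rate and its 95% CI based on the Clopper-Pearson method given various observed numbers of responders among the 30 patients", and concludes: "Thirty patients provide reasonably reliable estimates for hypothesis generation".

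Table 16, titled "Estimated PSA Response Rate and Its 95% CI for 30 Patients", has seven rows, from 6 to 24 responders in steps of 3. The row for 18 responders gives a response rate of 60% and a 95% interval of 40.60 to 70.34.

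Section 6.4.1 names the same method for the final analysis of the primary efficacy endpoint: "The PSA response rate will be calculated, and the 95% CI will be estimated using the Clopper-Pearson method".

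The synopsis repeats the claim about reliable estimates but does not reproduce the table, so the figure is not corrected elsewhere.

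**The concern.** The 60% row stands out by eye. At a fixed number of patients, Clopper-Pearson intervals are widest near 50% and narrow toward 0% and 100%. As printed, the 60% row is the narrowest of the seven, narrower even than the 20% and 80% rows.

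This matters because Part 2 is designed for estimation. Without a test, a power statement or a precision target, Table 16 is the only quantitative support that section 6.1 gives for 30 patients on the PSA response rate. The error is in the favourable direction. A reader of that row would conclude that 18 responders out of 30 rule out true response rates above about 70%, when rates up to about 77% remain compatible with such a result. If 18 responders were observed, the interval reported under section 6.4.1 would also disagree with the protocol.

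**Working it through.** **Inputs.** n = 30 (section 6.1 and the title of Table 16). Two-sided 95% confidence (Table 16). Clopper-Pearson method (sections 6.1 and 6.4.1). The split of 2.5% in each tail is the standard construction, and the reproduced rows confirm it.

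**Formulas**, for r responders out of n:

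- lower limit = 0.025 quantile of Beta(r, n − r + 1)
- upper limit = 0.975 quantile of Beta(r + 1, n − r)

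**Reproducing the table (limits in %, widths in percentage points).**

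| Responders | Printed limits | Recomputed limits | Width from printed limits | Recomputed width |
|---|---|---|---|---|
| 6 | 7.71, 38.57 | 7.71, 38.57 | 30.86 | 30.85 |
| 9 | 14.73, 49.40 | 14.73, 49.40 | 34.67 | 34.66 |
| 12 | 22.66, 59.40 | 22.66, 59.40 | 36.74 | 36.74 |
| 15 | 31.30, 68.70 | 31.30, 68.70 | 37.40 | 37.41 |
| 18 | 40.60, **70.34** | 40.60, **77.34** | **29.74** | **36.74** |
| 21 | 50.60, 85.27 | 50.60, 85.27 | 34.67 | 34.66 |
| 24 | 61.43, 92.29 | 61.43, 92.29 | 30.86 | 30.85 |

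Thirteen of the 14 limits agree to two decimals, including the lower limit of the 18-responder row. Differences of 0.01 in the widths are rounding.

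**Check 1: symmetry, using only printed figures.** Swapping responders and non-responders reflects the interval about 50%. For 18/30 the upper limit is the 0.975 quantile of Beta(19, 12), which equals 1 minus the 0.025 quantile of Beta(12, 19), and that quantile is the lower limit for 12/30. So:

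- upper limit for 18/30 = 100 − 22.66 = 77.34
- lower limit for 18/30 = 100 − 59.40 = 40.60

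The other mirror pairs in the table obey the rule. For 6 and 24 responders, 100 − 7.71 = 92.29 and 100 − 38.57 = 61.43. For 9 and 21, 100 − 14.73 = 85.27 and 100 − 49.40 = 50.60. The 15-responder row mirrors itself: 100 − 31.30 = 68.70.

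**Check 2: tail probability.** The upper limit is the rate p at which 18 or fewer responders out of 30 have probability 0.025.

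- At p = 0.7734 the probability is 0.0250, as required.
- At p = 0.7034 it is 0.149, about six times too large.
- At the lower limit, p = 0.4060, the probability of 18 or more responders is 0.0250, as required.

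**Check 3: another method or confidence level.** For 18/30:

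| Method | Interval (%) |
|---|---|
| Wald 95% | 42.47, 77.53 |
| Wilson 95% | 42.32, 75.41 |
| Agresti-Coull 95% | 42.29, 75.44 |
| Jeffreys 95% | 42.22, 75.95 |
| Clopper-Pearson 90% | 43.39, 75.05 |
| Clopper-Pearson 80% | 46.66, 72.27 |

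None gives 70.34, and none gives the printed lower limit of 40.60.

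**Size.** Printed width: 70.34 − 40.60 = 29.74 points. Correct width: 77.34 − 40.60 = 36.74 points. The shortfall is 36.74 − 29.74 = 7.00 points, and 7.00 / 36.74 = 19%.

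**The case against.** The case for treating this as a minor erratum is a fair one. One limit out of 14 is wrong. The least precise scenario, 15 responders with limits 31.30 and 68.70, is printed correctly, so a reader who judges 30 patients by the worst case is not misled. The mirror row, 12 responders, already shows the true width of 36.74 points. Section 6.1 sets no precision target or decision threshold, and the sample size was not derived from this limit. The rows are hypothetical, and the reported interval will be computed from the trial data, so the slip cannot bias a result.

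All of that stands, and it bounds the consequence. It does not make the printed figure right.

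Two further points have been raised. First, Part 2 enrolment is also tied to at least 15 patients with HR-intact tumors (section 3.1.1.2). That is a reason to extend enrolment and says nothing about the precision of the PSA response rate at 30 patients. Second, a single wrong digit could have arisen when the PDF was converted to text. This cannot be excluded without the page itself. The row is otherwise intact and its neighbours are exact, so a typing slip in the protocol is at least as plausible. It is a reason to check the source before amending.

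**Conclusion.** The printed upper limit for 18/30 is wrong: it should be 77.34%, not 70.34%. The arithmetic is certain, because it follows both from the method the plan names and from the table's own 12-responder row. The precision in that row is overstated by 7.00 points of width (19%), in the one table that supports the Part 2 sample size for the primary efficacy endpoint. The pattern suggests a one-digit slip.

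The error does not call 30 patients into question and does not touch the analysis method or any decision rule. The corrected width of 36.74 points is still below the 37.40 points already printed for 15 responders. The one assumption is that the digit stands in the protocol as it reads here.

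**What to change.** Confirm the figure against the protocol's source file. If it stands, change the 18-responder row of Table 16 from 40.60, 70.34 to 40.60, 77.34. No other row needs correction, and the text of section 6.1 can stay. The change is one number, can go into the next amendment, and costs only a less favourable precision figure in that row.
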